#### Clinician Administered Assessments:

**Structured Clinical Interview for DSM-IV (SCID)** [73]: Assessment used to determine psychiatric diagnoses. This interview assesses DSM-IV current and lifetime psychiatric diagnoses for anxiety, mood, psychotic, alcohol and substance use, somatoform, and eating disorders.

**Time-Line Follow-Back Assessment Method (TLFB):** [74] Interview technique that will be used to obtain quantity/frequency of alcohol consumption data for each day during the 90-day period prior to the study, throughout the period of study participation (measuring drinking on days outside of test session day) and the follow-up. Participants are given a blank calendar covering the time interval to be re-constructed and are asked to reconstruct retrospectively their drinking behavior over that interval. The process is facilitated by establishing anchor points (e.g., holidays, anniversaries, major national events, etc.). It can be scored to provide the number of days on which various levels of consumption occurred. The time-line method has good test-retest reliability and good validity for verifiable events. It has been used in numerous studies to compare pre- to post-treatment drinking.

#### Self-Rated Craving Measures:

**Alcohol Urge Questionnaire (AUQ)** [75]: The AUQ is an 8 item questionnaire, derived from a larger 49 item "Questionnaire of Alcohol Urges," that assesses *desire for a drink, expectation of positive effect from drinking, and inability to avoid drinking if alcohol was available*. The AUQ is a reliable and valid scale for the measurement of self-reported alcohol urges, and scores have been shown to be strongly related to alcohol dependence severity (as measured by ADS scores) and to cognitive preoccupation with alcohol. Its brevity and time frame for ratings (i.e., right now) makes it suitable for administration during the alcohol infusion period.

**Biphasic Alcohol Effects Scale (BAES)** [65]: The BAES is a 14-item self-report adjective rating scale that will be used to measure the stimulant and sedative effects of alcohol during the test sessions. This instrument has been found to be a sensitive and reliable measure to study medication influences on alcohol effects [76-78].

**Visual Analog Scales (VAS)**: In addition to sedation, the VAS has the following items that will also be assessed: craving for alcohol, high, anxious, drowsy, irritable, and nauseous. We recognize that single item scales may have greater variability than multiple item scales. However, they present a significant time saving advantage during busy test days. Many of these subjective measures have been utilized in several previous studies at our Center where they show very good sensitivity to drug effects and convergent validity with other measures of these mood states and symptoms.

**State Trait Anxiety Inventory (STAI-6)**: The STAI-6 is a 6 item measure designed to assess trait and state aspects of anxiety.

**C. Study Procedures:** All participants will be asked to arrive alcohol and drug free (except for marijuana) for the test session. Urine tests and a breathalyzer will be performed for verification. Those with positive urines or breathalyzer will be rescheduled one time. Additional non-compliance with this or any other procedure will result in discharge from the study. Since women will be recruited during the follicular phase of their menstrual cycle, they will be asked to call within the few days following the start of their menstrual bleeding to be scheduled for the laboratory session.

**Screening:** Potential participants responding to advertisements will be given a brief description of the study over the phone and will then be asked to complete a phone interview to determine their preliminary eligibility to participate in the study. If the caller appears to meet the eligibility criteria, he/she will be invited in for a 3 hour (approximate) screening session.\* During the screening visit, a detailed assessment will be completed to assess current health. Participants will be asked specifically about alcohol and drug use, and any traumatic experiences that they may have had. In addition, we will gather information about medical history, do an electrocardiogram (EKG), blood work (including pregnancy test for women), and urine will be tested for drugs of abuse (cocaine, marijuana, benzodiazepines, etc.). This information will become part of the participant's VA medical record. The screening will last approximately 2-3 hours.

**\*In order to reduce face-to-face interactions during COVID-19 potential participants will be given the option to complete a portion of the screening procedures remotely using a VA approved video platform (or by telephone when video is not feasible). If the psychological screening is conducted remotely, the participant will be mailed/mailed a blank consent form and an informed consent process with study staff will then take place either over the phone or via VA-approved video platform. We will go over the consent form in detail with the participants. Consents that are mailed will be sent using US Mail (USPS/UPS/FedEx). Consents that are e-mailed will be encrypted using a VA approved encryption platform (such as Azure).**

**A fully signed consent and HIPAA will be obtained prior to starting any screening procedures (remote or in-person) should they still be interested and eligible to continue in the study.** We will accept the following forms of signed consent and HIPAA: a) signed in person; b) signed at home and mailed back to the research team using a pre-addressed envelope; c) signed at home and the patient will take a photo of the consent and HIPAA pages and email the images to a member of the research team; or d) signed at home during a video visit where we will ask the patient to hold each consent and HIPAA page up to the camera and we will take a screenshot of the signature pages (ensuring the patient's face is not in view) and print and file the screenshots in the patient's research record.

- The following assessments will NOT be conducted remotely: physical exam, blood pressure/pulse, blood work, urine toxicology, pregnancy test, and EKG.

**Randomization:** Stratified block randomization will be used to balance treatment assignments within each gender. Our group has used this procedure with repeated success in previous and ongoing studies. The Research Pharmacy will create the randomization tables.

**Script Development:** Two scripts will be developed based on a procedure developed by Lang et al [79-81] and using Scene Construction Questionnaires [81-83]. The questionnaires elicit details on the event and individuals involved, including physical sensations, thoughts, emotions, and cues related to the event described. The stress related scripts will be based on the “most stressful” recent experience. Only stressful experiences rated 8 and above will be used for script development. Stressful experiences related to substance use will not be considered. The neutral script will be based on previously developed neutral scripts that will consist of a relaxed beach scene commonly experienced by most individuals but personalized for each participant. The script development can also be done virtually.

**Alcohol Clamp Procedure:** In this study, we will be using a modified alcohol-IV clamp procedure developed and standardized by Subramanian and colleagues [84], that has been used previously and in ongoing studies by the Co-PI [59]. We will use the latest state-of-the art infusion method CAIS that uses a computerized control of the alcohol infusion that includes real-time pharmacokinetic modeling to optimize the reliability and standardization of the procedure [85]. The infusion will be performed using a 6% ethanol solution in 0.9% saline. The computer assisted administration program automatically calculates and corrects the infusion rate based on real-time BrAc data entry by staff, based on the pharmacokinetic profile of each subject.

Alternatively, the alcohol-IV clamp procedure may be completed by using a MATLAB [86] calculation package. The loading phase rate, determined by MATLAB, will use a formula that includes patient age, gender, height, and weight to generate a linear ascension to target BrAc in 30 minutes. The infusion will still be performed using a 6% ethanol solution in 0.9% saline. BrAc will be measured during the loading phase as well as during the target BrAc clamp. Once the target BrAc is achieved, the infusion pump rate will be adjusted so that the subjects are maintained within  $\pm 5$  mg% of target BrAc for 30 minutes. In previous studies, this alcohol clamp method has been used safely and successfully to administer alcohol [57-60] in over 182 subjects.

**Participants will be required to have a negative COVID test within 3 days of the Test Day. Participants who can show proof (completed vaccination card) that they are fully vaccinated will not be required to have a COVID test prior to any of the test days,**

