***The goal of this Phase I study is to determine whether intravenous infusion of ALLO attenuates (1) stress-induced alcohol craving, stress-induced anxiety and (2) subjective stimulant/sedative effects of alcohol in individuals with AUD using a laboratory paradigm.*** The secondary objective of this project is to characterize the behavioral effects of ALLO in AUD. We propose a double-blind, randomized, between subject, placebo-controlled study in 60 individuals with AUD to compare *one dose (1.5 mg/ml solution) of continuous (200 min.) infusion of ALLO* (targeted plasma of 100 nM [IV bolus of 191 mcg/kg over 60 min. followed by continuous infusion of 57.4 mcg/kg/hr x 140 min.] n=30) to *placebo* (n=30). On a single test day, after 60 min of infusion - when ALLO levels stabilize - stress and neutral cues consisting of personalized 5 min. scripts will be presented in random order. The use of personalized scripts has been shown to produce robust and reliable craving and anxiety in subjects including heavy drinkers[1], alcohol dependent individuals (see the preliminary data section)[2] both with and without psychiatric comorbidity (including work by our group)[3-5] and, in those with other substance use disorders [6]. All participants will also receive alcohol administered intravenously using a clamp procedure, targeting a breath alcohol concentration (BrAc) of 40mg% (40 mg/dL). Alcohol will be administered following script presentation (20 min to target and clamped for

additional 30min). The main outcomes are measures of stress-induced alcohol craving, stress-induced anxiety, and subjective alcohol effects; other secondary outcomes include subjective mood effects, cognitive performance, and motor coordination.

**Hypothesis 1 (Specific Aim 1):** To determine if ALLO (targeted plasma of 100 nM), compared to placebo:

**Aim #1a:** attenuates stress-induced craving for alcohol, measured by the Alcohol Urge Questionnaire (AUQ).

**Aim #1b:** attenuates stress-induced anxiety, measured by the State Trait Anxiety Inventory (STAI-6).

**Aim #1c:** attenuates the subjective stimulant/sedative alcohol effects (target BrAC=40 mg%), measured by the Biphasic Alcohol Effects Scale (BAES).

**Hypothesis 2 (Specific Aim 2):** To characterize ALLO's behavioral effects:

**Aim #2:** to describe ALLO's subjective mood effects, we will use Differential Emotions Scale (DES-R), the Addiction Research Center Inventory (ARCI) and the Similarity to Drugs of Abuse Scale (SDAS).

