## 5. Research Plan:

**A. Our experience with laboratory stress-induced paradigms:** In a recent, randomized, within-subjects laboratory study, we compared the effects of neutral and stress cues (presented

**Overview:** This is a double-blind, placebo-controlled, between-subjects study with 1 test day. Subjects will receive intravenous ALLO infusion to achieve a targeted plasma (100 nM; N=30, n=15 men, 15 women) or placebo (PLA; N=30, n=15 men, n=15 women) in a randomized fashion. We recognize that the double-blind in the study may be compromised by the lack of an active placebo. However, ALLO side effects or their intensity have not been extensively studied at this dose. The dose of alcohol is also so low that possible side effects of alcohol are also very slim. In addition, our group has extensive experience conducting similar studies where, for example, high dose of alcohol (significantly higher than in this study) is compared to a placebo. In order to protect the blind for the participants we have combined the possible side effects for ALLO, alcohol and placebo. For each subject, the rate of infusion will be calculated based on their weight. After 60 min. of infusion, participants will be exposed to 2 conditions in random order: stress cues and neutral cues. The cues will consist of a 5 min. presentation of the stimulus (stress or neutral) followed by immediate evaluation of craving and anxiety. There will be a relaxation procedure between each condition (see Table in Human Subjects section), and the presentation of the second cue will be initiated after stress levels have decreased to baseline. During the first hour of infusion and before the start of the stress paradigm, all participants will complete a number of measures to characterize ALLO's effects on mood, cognitive performance and motor coordination. Following the script presentations all participants will receive IV alcohol (40 mg%) that will be infused over 20 min and clamped at a steady level for an additional 30 min (Study procedures are also presented in tabular form in the Human Subjects section). All subjects will make 2 visits, one to develop the scripts and one for testing. In order to control for baseline differences in ALLO we will study women in their follicular phase of the menstrual cycle when levels of ALLO are most stable. In the follicular phase, women have low ALLO levels that are comparable to those in men, < 1 nmol/L [61]. Women have higher ALLO levels than men in the luteal phase (> 4 nmol/L), and especially high during pregnancy (100 to 160 nmol/L)[62]. For females, all sessions will be scheduled within the first 4-7 days of a woman's menstrual cycle.

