#### **D. Data analysis and sample size considerations:**

Study data will be collected and managed using REDCap electronic data capture tools hosted at VA CT Healthcare System. REDCap (Research Electronic Data Capture) is a secure, web-based application designed to support data capture for research studies, providing 1) an intuitive interface for validated data entry; 2) audit trails for tracking data manipulation and export procedures; 3) automated export procedures for seamless data downloads to common statistical packages; and 4) procedures for importing data from external sources (Harris et al 2009).

**Data Analysis:** Descriptive statistics will be calculated and normality assumptions will be checked prior to analyses. Transformations or non-parametric methods will be used if normality assumptions are not satisfied. The primary analyses will use linear mixed models (LMMs). LMMs are flexible in modeling the variance-covariance structure of the repeated measures, use all available data on an individual, and provide unbiased and efficient results when data are missing at random. Based on Schwartz Bayesian information criterion (BIC) (smaller is better), we will select the appropriate correlation structure for each dependent variable. Medication will be entered as a categorical variable with two levels (placebo, ALLO 100 nM). Stress/Neutral cues will be entered as a within-subject variable with two levels: stress and neutral. Time will also be a within-subject factor (before cue presentation, and 2 times after each cue presentation). **Specific Primary Aims** will examine the effect of medication on craving (assessed with AUQ), and anxiety (assessed with STAI-6) under stress vs. neutral condition, and stimulant/sedative effects of 40 mg% alcohol. We will consider a significant interaction between medication and stress condition with smaller differences between the stress and neutral conditions on active drug (ALLO) supportive of our hypothesis. **Specific Secondary Aims** will examine the effect of medication, under stress vs. neutral, and in combination with alcohol on

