## 6. PROTECTION OF HUMAN SUBJECTS:

Human subjects: Non-treatment seeking individuals with AUD will be recruited from the New Haven area by newspaper advertisements, Craigslist, and flyers. Based on previous human laboratory studies, approximately 10 percent of the subjects who enroll in the study, meet all inclusion/exclusion criteria and are randomized are expected to either drop out or be terminated because of non-compliance with the study procedures. To meet the target sample of 60 completers, a total of 66 participants will be randomized. After the initial phone screening, potential subjects will undergo a comprehensive evaluation that is summarized in Table 1 in “Research Strategy”.

Study Procedures: Table 1 delineates the timeline for study procedures and measures that will be administered at each time point during the laboratory session.

Table 2. Study Procedures (times are approximate)

Time	Measures and Events
Baseline	Urine and BAC check, HR/BP, CIWA, TLFB, AUQ, STAI-6, VAS; BAES, NDS, DES-R, ARCI, SDAS, HVLT-R, Go no-Go, Grooved Pegboard Test, Ghrelin, NPY and ALLO levels, breakfast
-62 min	Ghrelin and NPY levels
-60 min	ALLO infusion starts
-40 min	HR/BP, AUQ, STAI-6, VAS; BAES, NDS, DES-R, ARCI, SDAS, HVLT-R, Go no-Go, Grooved Pegboard Test, ALLO levels
-20 min	HR/BP, ALLO levels
-2 min	Ghrelin and NPY levels
Stress Reactivity Condition 1 (15 min break)	
0 min	Condition 1. (Neutral or Stress) Baseline/Relaxation; BP & HR, AUQ, STAI-6, VAS
+10 min	Image period, BP & HR
+15 min	BP&HR, AUQ, STAI-6, VAS, Ghrelin and NPY levels
+20 min	Recovery period. AUQ, STAI-6, VAS
+25 min	BP&HR, AUQ, STAI-6, VAS, Ghrelin, NPY and ALLO levels

Stress Reactivity Condition 2	
+30 min	Condition 2. (Neutral or Stress). Baseline/Relaxation as described above
+40 min	Image Period as described above
+45 min	BP&HR, AUQ, STAI-6, VAS, Ghrelin and NPY levels
+50 min	Recovery Period as described above
+55 min	BP&HR, AUQ, STAI-6, VAS, BAES, NDS, DES-R, ARCI, SDAS, Ghrelin, NPY, and ALLO levels
Alcohol Infusion	
+70 min	start of IV alcohol infusion
+90 min	Target reached STAI-6, VAS, BAES, NDS, ARCI, SDAS, HVLT-R, Go no-Go, Grooved Pegboard
+118 min	Ghrelin and NPY draw
+120 min	IV alcohol infusion ends, ALLO infusion ends
+150 min	STAI-6, VAS, BAES, NDS, ARCI, SDAS, HVLT-R, Go no-Go, Grooved Pegboard, ALLO levels, Lunch

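### Cue order is neither stated to be balanced across arms nor included in the models: a small, cheaply avoidable loss of precision

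*Combined protocol and SAP*

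**What the plan says.** The Randomization paragraph (Research Plan, C. Study Procedures) reads "Stratified block randomization will be used to balance treatment assignments within each gender", followed by "The Research Pharmacy will create the randomization tables". Gender is the only stratifier named, and block size is not given.

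Each participant also receives a random cue order. The Overview of the Research Plan says that "participants will be exposed to 2 conditions in random order: stress cues and neutral cues", and the Purpose section says that the "scripts will be presented in random order". Neither place says how the order is generated or whether it is balanced by arm or gender.

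Under Data Analysis, "Stress/Neutral cues will be entered as a within-subject variable with two levels: stress and neutral". Time is the moment of rating relative to each cue, not whether that cue came first or second. Gender enters only for the exploratory aim. No order, period or sequence term appears for the AUQ, the STAI-6 or the BAES.

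In Table 2 (Protection of Human Subjects) either cue can occupy the second slot, and alcohol starts at +70 min for everyone. The Overview requires that "the presentation of the second cue will be initiated after stress levels have decreased to baseline". No similar condition is stated between the second cue and alcohol.

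**The concern.** Cue order can influence all three primary outcomes. For craving and anxiety (Aims 1a and 1b), position in the session may change the response to a script through habituation, fatigue or carry-over. That alters each person's stress-minus-neutral difference according to the order received. For the BAES (Aim 1c) there is one alcohol block per person, so order is purely a between-subject factor and cannot cancel within a person. Participants who heard the stress script second reach alcohol with a more recent stressor.

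If order is left unbalanced and unmodelled, its effect adds noise to every arm comparison. In a particular trial the arms may also end up with visibly different order mixes. The trial is small (30 per arm, 15 per arm within gender), so such splits are not rare. The gender-by-treatment comparisons of Aim 4 rest on the smallest cells.

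**Working it through.** **Inputs.** From the documents: 30 per arm and 15 per arm within gender (Overview); two-sided alpha 0.05 and a detectable d = 0.74 with at least 80% power (Data Analysis and Sample size considerations); session times (Table 2). Assumed: order drawn independently at 1:1, and an order effect *w*. Here *w* is the gap between the two orders in mean outcome, in units of the SD within an order. The documents give no value for *w*.

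**The plan's own figure.** With 30 per arm and d = 0.74, the noncentrality is 0.74 x sqrt(30/2) = 2.87. A two-sided t test on 58 df then has 80.5% power, so the stated figure reproduces.

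**How often the arms differ in order.** The stress-first counts are two independent Binomial(30, 0.5) variables. The SD of their difference is sqrt(2 x 30 x 0.25) = 3.87. Exact probabilities:

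- difference of at least 4: 36.6%
- difference of at least 6: 15.5%
- difference of at least 8: 5.2%
- within one gender (15 per arm), at least 4: 20.0%; in at least one gender, 1 - (1 - 0.200)^2 = 36%

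If order were balanced 30/30 overall but not by arm, a difference of at least 6 would occur in 19.6% of trials.

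**Average loss of precision.** A 1:1 random order adds w^2/4 to the outcome variance, so the sampling SD of the arm contrast grows by sqrt(1 + w^2/4).

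| Outcome | Assumed w | Factor |
|---|---|---|
| BAES (Aim 1c) | 0.25 | 1.008 |
| BAES (Aim 1c) | 0.5 | 1.03 |
| Stress-minus-neutral difference (Aims 1a, 1b) | 0.5 | 1.03 |
| Stress-minus-neutral difference (Aims 1a, 1b) | 1.0 | 1.12 |

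For Aims 1a and 1b, a position effect *p* raises the difference in one order and lowers it in the other, so w = 2p.

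**Shift given a bad split.** With 18 versus 12 stress-first, the BAES contrast moves by (18 - 12)/30 x w = 0.2w. That is 0.05 SD at w = 0.25 and 0.10 SD at w = 0.5, or 7% and 14% of d = 0.74.

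**Timing.** The script ends at +15 min (first slot) or +45 min (second slot).

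| Event | Stress second | Stress first |
|---|---|---|
| Alcohol starts, +70 min | 25 min | 55 min |
| First BAES under alcohol, +90 min | 45 min | 75 min |
| Last BAES, +150 min | 105 min | 135 min |

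Table 2 calls its times approximate.

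**What adjustment costs.** With an 18 versus 12 split, adding order as a covariate removes an additive shift. The variance factor is 1/(1 - 0.2^2) = 1.04, about 2% in the standard error.

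**Why blocking alone is not enough.** Balanced order removes w^2/4 from the true sampling variance. Without an order term the residual variance still contains it, so the reported standard error stays too large by the factors in the first table.

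**The case against.** The strongest reply is that the documents do not say order is unblocked. A counterbalanced list is also a random order, and the pharmacy may already use one. That stands: simple randomisation is the natural reading but an inference, and every imbalance probability above depends on it.

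A reader might infer that the Aim 1c comparison is biased or its type I error inflated. The documents do not support that. Order is randomised independently of treatment, so the comparison is unbiased over randomisations and the ordinary standard error already carries the order noise. One can compute a conditional type I error of 11.9% and power of 54%. Those figures require an 18 versus 12 split and a 1.0 SD order effect on the BAES, which is larger than the planned drug effect of 0.74 and has no source in the documents.

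A reader might also take 25 versus 55 min as the exposure gap. That runs to "start of IV alcohol infusion"; the gap that matters for the outcome is 45 versus 75 min to the first BAES under alcohol. A recovery period follows the second script, and BAES, STAI-6 and VAS are taken at +55 min, so residual stress just before alcohol is measured. Carry-over may be small.

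Nor does Aim 1c depend on restricted allocation, since an order covariate handles an additive effect. Aim 4 is declared exploratory. What survives is that the plan states neither remedy, and both are nearly free.

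**Conclusion.** The point holds as a minor improvement. Treatment is blocked within gender, cue order is described only as random, and the models omit it. The expected cost is about 1-3% in sampling SD for Aim 1c and 3-12% for the medication-by-cue contrast of Aims 1a and 1b. If order is simply randomised, there is also a 15.5% chance of an arm difference of at least 6 of 30. The first such split, 18 versus 12, would shift the BAES contrast by 0.05-0.10 SD.

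These sizes rest on assumed order effects (0.25-0.5 SD for the BAES; 0.5-1 SD of the stress-minus-neutral difference for Aims 1a and 1b). If order has no effect, nothing is lost. If the pharmacy already balances order by arm, what remains is to say so and to add the model terms. The validity of the primary tests is not in question, and the sample size need not change.

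**What to change.** 1. State how cue order is generated. For participants not yet randomised, have the Research Pharmacy generate treatment and order together. Within each gender, use permuted blocks of varied size (multiples of four) over the four combinations of ALLO or placebo with stress-first or neutral-first. Release the order to session staff separately from the treatment code.
2. Add cue position (first or second) to the AUQ and STAI-6 models, and cue order as a between-subject covariate to the BAES model. Specify both before unblinding. For participants already randomised, these terms alone recover most of the gain, provided the order each person received is recorded.

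The cost is small but not zero. The tables become slightly more complex, and each model spends one degree of freedom. Some blocks will be incomplete, because 30 per gender is not a multiple of four. Predictability also rises a little. In a joint block of eight, each order holds two ALLO and two placebo assignments. Staff who know the order, the block size and the earlier treatments could deduce the last assignment in each order: two of eight, against one guaranteed in a treatment-only block of eight. Varying the block size and withholding it from session staff limits this, which matters because the Overview concedes that the blind may be compromised.
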